9.4.6 Pharmacokinetics

The following PK parameters will be calculated from plasma concentrations of RPL554 using standard non-compartmental methods.

- Part A: AUC_{0-t} represents the area under the plasma concentration curve from time 0 to last observed value above the lower limit of quantification
- Part A: Half-life=ln(2)/λ_z
- Parts A and B: AUC_{0-12h} represents the area under the plasma concentration curve from time 0 to 12 hours. The AUC_{0-12h} value after dose 13 in Part B is considered an appropriate

estimate of the AUC at steady state. C_{max} denotes the highest plasma concentration measured

- t_{max} denotes the time point corresponding to C_{max}

PK parameters will be summarized by dose level using descriptive statistics (n, geometric mean, coefficient of variation [CV], minimum, maximum and median for AUC parameters, C_{max} , n, arithmetic mean, standard deviation, minimum, maximum and median for t_{max}).

In Part A, dose-normalized parameters (AUC_{0-t} and AUC_{0-12h}, C_{max}) will be compared using analysis of variance models with fixed factor treatment. In Part B, dose-normalized AUC_{0-12h} and C_{max} will be compared using analysis of covariance models adjusting for factors treatment, period and patient 90% confidence intervals will be constructed for the geometric mean ratios. If appropriate, AUC_{0-12h} data from Parts A and B belonging to the same patient and the same dose of RPL554 may be combined to compute the accumulation index (repeat dose/single dose ratio).

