3.2 Discussion of Study Design, including the Choice of Control Groups

Part A is designed as a single dose, parallel group study to evaluate the safety and terminal PK profile of a range of doses of RPL554 in a new DPI formulation compared to placebo. The safety and bronchodilatory response following a single dose will also be assessed.

In Part A, five dose levels ranging from 150 µg up to 6000 µg have been selected to evaluate the safety, PK and efficacy/pharmacodynamic characteristics of this formulation over a dose range covering a 40-fold increase in doses. A total of approximately 36 COPD patients aged 40 to 80 years (inclusive) will be randomized. Patients in Part A will be randomly assigned to receive either RPL554 or placebo via DPI. Following an analysis of the safety, PK and efficacy/pharmacodynamics, four doses will be selected for Part B. Study medication administered via DPI will be double blind, except for the 6000 µg treatment arm in Part A which

will be single blind due to the number of capsules required, in order to minimize any potential bias in the overall assessment of treatment effect and safety.

Part B is designed as a crossover study to assess the steady state efficacy/pharmacodynamic effect of four dose levels of RPL554 administered by DPI after a week of twice daily dosing, and to compare that effect with placebo DPI. Steady state PK and safety will also be assessed. One week of treatment was selected to evaluate efficacy/pharmacodynamics, PK and safety at steady state, as clinical data to date has shown that steady state PK is achieved after approximately 3 days of twice-daily dosing with the nebulized formulation.

In Part B, all patients from Part A will undergo five treatment periods in a double-blind randomized, crossover design; therefore, each patient will act as his or her own control. This design makes it possible to obtain unbiased inferences about differences between treatments, based on intra-patient differences.

The washout period between the treatment periods has been selected based upon the available PK of RPL554 in healthy volunteers, and patients with asthma or COPD. Five half-lives is considered as the time for elimination of RPL554 from the body. In this study, a washout period of 7 to 10 days from the last dose of study medication has been deemed adequate to ensure there was no overlap between the PK profiles of treatments with RPL554 in consecutive treatment periods.

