5.3 Selection of Doses and Dosing Schedule

5.3.1 Selection of Doses in the Study

The doses of RPL554 have been selected to cover a 40-fold dose range of the DPI formulation.

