  MODEL PARAMETER = TREATMENT;
  ESTIMATE 'LOGTREATMENT - 1 unit' TREATMENT 1/CL ALPHA=0.1;
  ODS OUTPUT ESTIMATES = ESTIMATE;
  ODS OUTPUT SOLUTIONR = SOLUTION;
RUN;
```

where PATIENT = patient ID

PARAMETER = separate models for each of the log(parameters): log(AUC_{0-12h}) log(AUC_{0-t}) and log(C_{max})

TREATMENT = log (treatment group [RPL554 treatment groups])

Document: Z:\RPL554\AZA40375\Biostatistics\Documentation\SAP\Verona RPL554-DP-201 SAP v1.0 – Part A

Author: [name]

Version Number: 1.0

Version Date: [19DEC2018]

Template No.: CS_TP_BS016 Revision 5

Reference: CS_WI_BS005

Effective Date: 01Apr2018

Copyright © 2009, 2010, 2012, 2016, 2018 IQVIA. All rights reserved. The contents of this document are confidential and proprietary to IQVIA Holdings Inc. and its subsidiaries. Unauthorized use, disclosure or reproduction is strictly prohibited.

Summary statistics (For AUC and C_{max} parameters: n, geometric mean, coefficient of variation [CV], minimum, maximum and median and for t_{max} parameter: n, arithmetic mean, standard deviation, minimum, maximum and median) will also be presented.

Document: Z:\RPL554\AZA40375\Biostatistics\Documentation\SAP\Verona RPL554-DP-201 SAP v1.0 – Part A

Author: [name]

Version Number: 1.0

Version Date: [19DEC2018]

Template No.: CS_TP_BS016 Revision 5

Reference: CS_WI_BS005

Effective Date: 01Apr2018

Copyright © 2009, 2010, 2012, 2016, 2018 IQVIA. All rights reserved. The contents of this document are confidential and proprietary to IQVIA Holdings Inc. and its subsidiaries. Unauthorized use, disclosure or reproduction is strictly prohibited.

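### Part A compares AUC0-t between doses, but its time window ends at the assay limit; if low-dose samples fall below that limit, proportional exposure will look more than proportional

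*Protocol*

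**What the plan says.** Protocol 9.3.1.1 lists AUC0-t among the Part A primary endpoints, with AUC0-12h, Cmax, tmax and half-life. Section 9.4.6 defines two areas. One has a floating end: "AUC_{0-t} represents the area under the plasma concentration curve from time 0 to last observed value above the lower limit of quantification". The other has a fixed end: "AUC_{0-12h} represents the area under the plasma concentration curve from time 0 to 12 hours".

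Both enter the same comparison: "In Part A, dose-normalized parameters (AUC_{0-t} and AUC_{0-12h}, C_{max}) will be compared using analysis of variance models with fixed factor treatment". Section 3.2 says that "five dose levels ranging from 150 µg up to 6000 µg have been selected", "over a dose range covering a 40-fold increase in doses".

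Part A SAP section 17 repeats both definitions. It dose-normalises the same three parameters and adds a power model, with "separate models for each of the log(parameters" AUC0-12h, AUC0-t and Cmax. Proportionality is judged by a slope near 1, and the code requests a 90% confidence interval.

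Neither document gives a common last time for AUC0-t, an AUC0-inf, a display of the last quantifiable time, or a rule for plasma concentrations below the limit. Section 17 rules out imputation of missing data. The conversion of below-limit results in SAP section 16.2 is for safety laboratory tests.

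**The concern.** Under proportional kinetics the 150 µg concentration at any time is 1/40 of the 6000 µg concentration. It must therefore reach a common assay limit at the same sample or an earlier one. When it is earlier, dose-normalised AUC0-t sets a short area at the low dose against a 24 h area at the high dose.

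The bias runs in one direction: low-dose exposure is understated, so exposure seems to rise faster than dose. More patients would not remove it, because it comes from the definition of the parameter. At stake is a false statement about dose proportionality based on a named primary endpoint. The plan does not say which of the three parameters governs if they disagree.

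**Working it through.** **The plan's own figure.** 6000/150 = 40, as stated.

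**Inputs from the documents**
- Active doses 150, 500, 1500, 3000 and 6000 µg, about 6 patients each (Protocol 5.1.1).
- Samples at 0.25, 0.5, 1, 1.5, 2, 4, 8, 12 and 24 h (Protocol 6.3.3).
- Half-life about 10 to 12 h, from the nebulised product (Protocol 1.1).
- 90% interval for the slope (Part A SAP 17).

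**Assumed, because not given:** the assay limit, the dry-powder concentrations, mono-exponential decay, and a between-patient CV of 30% to 50%.

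**Step 1: area lost.** With k = ln2/half-life, AUC(0-t)/AUC(0-24) = (1 − e^(−kt))/(1 − e^(−24k)).

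| Last quantifiable time | Half-life 10 h | Half-life 12 h | Apparent 6000/150 ratio, dose-normalised |
|---|---|---|---|
| 24 h | 1.00 | 1.00 | 1.00 |
| 12 h | 0.697 | 0.667 | 1.44 to 1.50 |
| 8 h | 0.525 | 0.493 | 1.90 to 2.03 |

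**Step 2: effect on the slope.** The slope is fitted to log AUC on log dose with an intercept. For the five doses, mean ln(dose) = 7.049 and the sum of squares about it is 8.562. The 150 µg arm has weight (5.011 − 7.049)/8.562 = −0.238. If only that arm is shortened, slope = 1 − 0.238 × ln(fraction from step 1).
- Stops at 12 h: 1 + 0.238 × 0.361 = 1.09; 1 + 0.238 × 0.405 = 1.10.
- Stops at 8 h: 1 + 0.238 × 0.644 = 1.15; 1 + 0.238 × 0.707 = 1.17.

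**Step 3: precision.** The log-scale SD is √ln(1 + CV²), which is 0.294 at CV 30% and 0.472 at CV 50%. SE = SD/√(6 × 8.562) = 0.041 to 0.066. With 28 degrees of freedom t = 1.701, so the half-width is 0.07 to 0.11. A slope of 1.09 to 1.10 would on average exclude 1 at the lower CV but not at the higher. A slope of 1.15 to 1.17 would exclude 1 across that range.

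**Step 4: when truncation starts.** Under mono-exponential decay the 24 h concentration is e^(−24k), or 19% to 25% of the initial value. An assay limit below that share of the 150 µg Cmax causes no truncation, leaving between-patient variation aside. If only 30% of the initial concentration follows the slow phase (an assumed bi-exponential profile), the threshold falls to 0.3 × 19% to 0.3 × 25%, about 6% to 8%. Adding absorption to these profiles moves the thresholds to 22% to 29% and 9% to 12%.

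**Step 5: simulated error rate.** The settings were exact proportionality, 6 per dose, CV 40%, half-life 12 h, trapezoidal areas on the protocol times and 800 runs. With an assay limit at 20% of the 150 µg Cmax, the 90% interval lies wholly above 1 in 10% of runs (one-compartment) or 51% (bi-exponential), against 5% nominal. At 2% to 5% of that Cmax the rate is 4% to 6%. A common 0-24 h window, as if no limit applied, gives about 2% to 6% throughout.

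**The case against.** The strongest reply is that the main safeguard is already planned. AUC0-12h and Cmax go through the same comparisons, Cmax is not shortened, and AUC0-12h is unaffected while the 12 h sample is quantifiable. A disagreement between AUC0-t and AUC0-12h would show in the planned output. That stands, and it limits the problem to one of three parallel parameters. It does not settle which parameter governs. Nor does it help if 150 µg is lost before 12 h, when AUC0-12h also lacks a rule.

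The consequence is also limited. Part A's primary objective is to describe the PK profile (Protocol 2.1.1), and the SAP sets no acceptance limits for the slope. All four lower doses go into Part B, with a ceiling set in advance (Protocol 5.1.2). A reader might infer that a biased slope drove dose selection; the documents tie no decision to it.

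Two other stronger readings are tempting.
- *That low doses are in fact cut short.* Protocol 7.3 says only that the assay is validated, and the half-life comes from another formulation. Truncation is possible but not shown.
- *That several low doses stop at staggered times*, such as 8 h at 150 µg and 12 h at 500 µg (slope about 1.20), or 4, 8 and 12 h at the three lowest doses (about 1.35). Under proportional mono-exponential decay with one assay limit, 500 µg stays quantifiable ln(500/150)/k = 17 to 21 h longer than 150 µg. If 150 µg is still measurable at 8 h, 500 µg is measurable at 24 h, so the first pattern cannot arise; nor can the second. Slopes of that size need other assumptions. The assumed bi-exponential profile gives 1.24 to 1.25 with a limit at 30% of the 150 µg Cmax, and 1.37 to 1.39 at 50%.

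**Conclusion.** The concern holds conditionally. The definition, the 40-fold range and the direction of bias come from the documents; whether truncation occurs does not. If every arm is quantifiable to 24 h there is no bias. Otherwise, under the mono-exponential assumption with a 10 to 12 h half-life, the slope is inflated by about 0.09 to 0.10 (150 µg stopping at 12 h) or 0.15 to 0.17 (stopping at 8 h). That is similar to or larger than the 0.07 to 0.11 half-width. Faster early decline would bring truncation on at lower assay limits. AUC0-t is therefore an unsafe basis for inference on proportionality under this plan. The damage is confined to that parameter provided the 12 h sample at 150 µg is quantifiable.

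**What to change.** Amend Part A SAP section 17, and note the change against Protocol 9.4.6:

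1. State that the proportionality conclusion rests on Cmax and AUC0-12h.
2. Keep AUC0-t as a descriptive summary, with the last quantifiable time tabulated by dose.
3. State how plasma values below the limit enter the areas.
4. Name a fixed shorter common interval, for example AUC0-8h or AUC0-4h, to be used at every dose if the lowest dose is not quantifiable to 12 h, with the condition that triggers it. Naming it in advance avoids choosing the interval from the results.

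AUC0-inf is a weak substitute: under the step 1 assumptions it extrapolates 19% to 25% of the area even when all 24 h samples are quantifiable.

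Items 3 and 4 belong before concentrations are unblinded. The protocol amendment reports Part A complete and selected data analysed. If that point has passed, the change should be labelled post hoc and justified in the study report, as Protocol 9.1 requires for deviations.

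The cost is SAP wording and minor reprogramming, and AUC0-t loses its inferential comparison. No new data are needed.

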9.4.7 Safety

Safety data including laboratory safety tests, 12-lead ECG, vital signs and physical examinations, will be summarized by treatment group and timepoint of collection, when appropriate, for each of the two parts separately. For continuous variables, the change from baseline (pre-dose at each treatment period) to each post-dose time point will also be calculated and summarized. Data will further be illustrated by shift tables (showing changes from low/normal/high) and shift plots for selected time points. Separate listings will be generated of abnormal values occurring after the first dose of study treatment.

In Part A, change from baseline in peak pulse and peak heart rate will be compared between the treatments using analysis of covariance models with fixed factor treatment, and using the pre-dose baseline value as a covariate. In Part B, change from baseline in peak pulse will be compared between the treatments using analysis of covariance models with fixed factors for treatment, period and patient, and using the pre-dose Day 1 baseline value as a covariate. Additive model will be used for pulse and heart rate.

Coded adverse event terms will be presented by system organ class (SOC) and preferred term and summarized by treatment group for each part. Summary tables by treatment group with total number and number of patients with adverse events, SAEs, adverse events leading to discontinuation of study treatment, causally related adverse events and severe adverse events will be produced. Further SAEs, causally related adverse events and adverse events of each intensity will be summarized by SOC and preferred term.

9.4.8 Handling of Withdrawals or Missing Data

In Part B, patients withdrawn after only one treatment period will not be included in the efficacy/pharmacodynamic and PK analyses of parameters that can be computed in all planned treatment periods. Imputation of data for calculation of average (AUC) effects for FEV₁ will be described in the statistical analysis plan. No other imputation of missing data will be performed.

All available data from all dosed patients who have received study treatment will be listed and summarized. Any unscheduled or unplanned readings will be presented within the patient listings, but only the scheduled readings will be used in any summaries. If a visit is rescheduled

due to variability in FEV₁ or other reason, the rescheduled visit will be listed and summarized as the valid visit.

9.4.9 Interim Analyses

No formal interim analysis is currently planned. This study will consist of two separate and independent analyses. To avoid possible effects of the unblinding of data from Part A on the blinding in Part B, only aggregated data (i.e. treatment level, without individual patient identifiers) will be revealed at the time of the analysis of the Part A data.

9.5 Determination of Sample Size

The sample size is determined for Part B. This is a complete block crossover study. Assuming a residual CV of 6% for peak FEV₁, 30 patients will give an 80% power to detect a pairwise difference in peak FEV₁ of 4.6%. Assuming a mean baseline FEV₁ of 1.5 L this will correspond to a difference of about 70 mL. To account for withdrawals, 36 patients will be randomized to Part A.

10 ETHICAL CONSIDERATIONS

10.1 Guidelines

The study will be performed in accordance with ICH GCP guidelines, the principles outlined in the Declaration of Helsinki (1996), the protocol and applicable regulatory requirements.

10.2 Ethics and Regulatory Approval

The Sponsor will supply all background data necessary to enable submission to the appropriate IRBs and regulatory authorities. The study will not commence before formal ethical and regulatory approvals have been granted.

All changes or revisions of this protocol will be documented. The reason for the amendment will be stated. The Sponsor will ensure ethical and regulatory approval is obtained for all substantial amendments to the original approved documents.

10.3 Informed Consent Process

It is the responsibility of the Investigator to obtain written informed consent from patients. All consent documentation must be in accordance with applicable regulations and ICH GCP. Each patient is requested to sign and date the informed consent form after (s)he has received and read the patient information sheet and received an explanation of what the study involves, including but not limited to: the objectives, potential benefits and risk, inconveniences and the patient's rights and responsibilities. Patients will be given adequate time to evaluate the information given to them before signing the informed consent form.

One original of the signed informed consent form must remain on file and must be available for verification by the study monitor at any time. A second original of the informed consent form plus the patient information sheet must be given to the patient or the patient's legally authorized representative.

10.4 Patient Confidentiality

Data collected during this study may be used to support the development, registration or marketing of the study medication. The Sponsor will control all data collected during the study and will abide by the European Union Directive on Data Privacy concerning the processing and use of patient's personal data. For the purpose of data privacy legislation, the Sponsor will be the data controller.

After patients have consented to take part in the study, their medical records and the data collected during the study will be reviewed by the Sponsor and/or its representatives. These records and data may, in addition, be reviewed by the following: independent auditors who validate the data on behalf of the Sponsor; regulatory authorities and the IRB which gave its approval for this study to proceed.

Although patients will be known by a unique number, their initials will also be collected and used to assist the Investigator to reconcile data clarification forms, for example, that the results of study assessments are assigned to the correct patient. The results of this study containing the unique number, but not the patient's initials and relevant medical information may be recorded

and transferred to and used in other countries throughout the world, which may not afford the same level of protection that applies within the European Union. The purpose of any such transfer would be to support regulatory submissions made by the Sponsor in such countries.

10.5 Record Maintenance/Retention

The Investigator will retain the originals of all source documents generated at the location where the study is being conducted, either: 1) until after regulatory agency approval is obtained for the study medication in the country/countries in which the results of this study comprise the submission dossier, or 2) for a period of 2 years after the report of the study has been finalized, in the absence of a regulatory approval. After that time, all study-related documents will be archived according to ICH GCP regulations.

11 FINANCE AND INSURANCE

Financial arrangements are detailed in the Investigator Agreement between the Sponsor and Investigator.

The Sponsor will arrange clinical study insurance to compensate patients for any potential injury or death caused by the study.

12 PUBLICATION POLICY

The publication policy is detailed in the Investigator Agreement between the Sponsor and Investigator.

14 APPENDICES

14.1 Birth Control Methods for Women of Childbearing Potential Which May Be Considered As Highly Effective

(Adapted from the [Clinical Trial Facilitation Group, Heads of Medicines Agencies, 2014](#))

I. Definitions

Woman of Childbearing Potential

A woman is considered fertile following menarche and until becoming postmenopausal unless permanently sterile. Permanent sterilization methods include hysterectomy, bilateral salpingectomy, and bilateral oophorectomy.

Women in the following categories are not considered women of childbearing potential:

1. Premenopausal female with one of the following:
 - Documented hysterectomy
 - Documented bilateral salpingectomy
 - Documented bilateral oophorectomy

Note: Documentation can come from the study center staff's: review of participant's medical records, medical examination, or medical history interview.

2. Premenarchal
3. Postmenopausal female

Females who are postmenopausal (age-related amenorrhea ≥ 12 consecutive months and increased FSH >40 mIU/mL), or who have undergone hysterectomy or bilateral oophorectomy are exempt from pregnancy testing. If necessary to confirm postmenopausal status, an FSH will be drawn at Screening.

Females on hormone replacement therapy (HRT) and whose menopausal status is in doubt will be required to use one of the non-hormonal highly effective contraception methods if they wish to continue their HRT during the study. Otherwise, they must discontinue HRT to allow confirmation of postmenopausal status before study enrollment.

II. Methods

For the purpose of this guidance, methods that can achieve a failure rate of less than 1% per year when used consistently and correctly are considered as highly effective birth control methods. Such methods include:

- Combined (oestrogen and progestogen containing) hormonal contraception associated with inhibition of ovulation:
 - Oral
 - Intravaginal
 - Transdermal

- Progestogen-only hormonal contraception associated with inhibition of ovulation ¹:
 - Oral
 - Injectable
 - Implantable ¹
- Intrauterine device ¹
- Intrauterine hormone-releasing system ¹
- Bilateral tubal occlusion ¹
- Vasectomized partner ^{1,2}
- Sexual abstinence ³

¹ Contraception methods that in the context of this guidance are considered to have low user dependency

² Vasectomised partner is a highly effective birth control method provided that partner is the sole sexual partner of the trial participant and that the vasectomized partner has received medical assessment of the surgical success

³ In the context of this guidance sexual abstinence is considered a highly effective method only if defined as refraining from heterosexual intercourse during the entire period of risk associated with the study treatments. The reliability of sexual abstinence needs to be evaluated in relation to the duration of the clinical trial and the preferred and usual lifestyle of the patient

